### 10.3. Definition of Baseline

Unless otherwise specified, baseline is defined as the measurement closest to the date of the first administration of Investigational Medicinal Product (IMP), and preceding the first dose of IMP (MN-001 or Placebo).

For the DBT Phase, baseline values will be assessed pre-dose at Visit 3 (Day 1) in this study. For pulmonary function test, 6MWT, MMRC, ATAQ-IPF and 12-Lead ECG, the baseline values will be assessed at Visit 2 (Day -7).

For the OLE Phase, unless otherwise specified, baseline values for those subjects who were taking Placebo in the DBT Phase will be defined as measurements closest to the first administration of MN-001 and preceding the first dose of MN-001. Therefore, these baseline values will be the ones assessed pre-dose on Visit 8 (Month 6) of the DBT phase.

#### 10.4. Definition of Visit Windows

The same visit windows will be used as defined in the protocol.

#### 10.5. Multicentre Studies

This is a single-center study.

### 10.6. Multiple Comparisons and Multiplicity

The results of all statistical tests (i.e., P values) will be interpreted descriptively, and no adjustment for multiple comparisons will be made.

### 10.7. Planned Subgroup Analyses

No subgroup analyses are planned in this study.

### 10.8. Analysis Software

All analysis will be performed using SAS® Software version 9.4 or above.

### 11. STUDY SUBJECTS

#### 11.1. Disposition of Subjects and Withdrawals

All subjects who provide informed consent will be accounted for in this study. The number of screen failures will be presented. The number and proportion of subjects in each analysis set will be presented by treatment arm (in percentage of the number of subjects randomized) and overall. The number and

proportion of completers will be presented by treatment arm and overall. The number and proportion of early withdrawals will be presented by the coded term for main reason of withdrawal and overall, by treatment arm and overall.

Subjects who are in the Safety Analysis Set but not in the Full Analysis Set will be listed.

Randomization errors will be listed.

#### 11.2. Protocol Deviations

The number and proportion of subjects with protocol deviations will be presented by treatment arm, for each coded term.

All protocol deviations will be listed.

#### 11.3. Inclusion and Exclusion Criteria

Subjects who meet all the inclusion criteria and none of the exclusion criteria are eligible to participate in the clinical trial.

Deviations from inclusion/exclusion criteria will be listed.

#### 12. DEMOGRAPHICS AND OTHER BASELINE CHARACTERISTICS

### 12.1. Demographics

For variables assumed to be continuous, like age at screening, body weight and height descriptive statistics will be prepared by treatment arm, for each analysis set separately.

For categorical variables like gender, race, ethnicity, frequency tables (n and percentage) will be prepared by treatment arm, for each analysis set separately.

All demography data will be listed.

#### 12.2. Prior and Concomitant Medications

Prior medications/therapies are defined as those for which the end date is prior to the date of first IMP administration. Concomitant medications/therapies are defined as those with start date on or after the date of first IMP administration and those with start date prior to the first IMP use but with end date on or after the date of first IMP administration.

Concomitant medications entered into the database will be coded using the most recent version of the World Health Organization Drug Dictionary which employs the Anatomical Therapeutic Chemical (ATC) classification system. The number and percentage of subjects who took prior and concomitant medications will be summarized separately by ATC classification first level (alphabetically), ATC classification second level (in decreasing order of frequency) and treatment arm.

These therapeutics will be listed by subject along with their classification, indication of the treatment, total daily dose and start and stop date of the treatment.

The number and percentage of subjects who took prior and concomitant treatments will be presented separately.

All prior and concomitant medication data will be listed.

#### 12.3. Baseline and Screening Conditions

Baseline and Screening condition data will be assessed by treatment arm using descriptive statistics. No inferential test statistics are planned for baseline comparison of the treatment arms.

#### 12.3.1. Baseline Medical History

All medical history events and their details will be listed. The number and percentage of subjects in different medical history categories will be presented by treatment arm.

### 12.4. Measurement of Treatment Compliance

Number of prescribed and taken capsules will be calculated and listed.

Compliance will be assessed by counting capsules and dividing the actual number of doses taken (per capsule count) by the number of doses the subject should have taken within a visit period and multiplying by 100.

Subjects who miss more than 25% of scheduled doses or take more than 125% of the scheduled doses will be considered noncompliant and may be discontinued from the study per investigator's judgment.

Descriptive statistics for treatment compliance will be provided. Number of subjects with low compliance (<75%) and with too high compliance (>125%) will be presented by treatment arm.

Start date of the dosing period, dose, dosing frequency and number of dosing days will be listed.

#### 13. EFFICACY ANALYSIS

Efficacy analysis will be performed on the Full Analysis Set. All efficacy measurements will be listed.

### 13.1. Primary Efficacy Variable Analysis(s)

The primary efficacy endpoints are the absolute and relative change from baseline in FVC and FVC% predicted up to 26 weeks, and the semiannual decline of disease activity based on FVC. To estimate the semiannualized rate of change in FVC between baseline and Month 6, a random intercept, random slope linear mixed model will be fitted (using proc mixed in SAS). Missing data will not be imputed because the ML-estimate is unbiased for this model in case of a Missing at Random (MAR) mechanism.

The model equation is the following:

$$Y_{ij} = \alpha + \beta_1 t_{ij} x_{1i} + \beta_2 t_{ij} x_{2i} + a_i + b_i t_{ij} + \varepsilon_{ij}$$

where:

 $Y_{ij}$  is the FVC value for the  $\mathrm{i}^{\mathrm{th}}$  subject at the  $\mathrm{j}^{\mathrm{th}}$  time point

 $\alpha$  is the common intercept

 $t_{ij}$  denotes time point j for the ith subject (actual time in half-years)

 $x_{1i}$  = 1 if subject *i* is in the active treatment arm, and 0 otherwise

 $x_{2i}$  = 1 if the subject *i* is in the placebo arm, and 0 otherwise

 $a_i$  and  $b_i$  are random effects (random intercepts and slopes) for subject i

Statistical Analysis Plan v1.0

Protocol Short Title: A Study of MN-001 in Subjects with

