13. STATISTICS

The Statistical Analysis Plan (SAP) will provide comprehensive details on the statistical methods planned for this study.

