**Idiopathic Pulmonary Fibrosis** 

 $\varepsilon_{ij}$  is a random error term

The following null hypothesis (equal mean rates of change) will be tested within this model:

$$H_0: \beta_1 = \beta_2$$

The alternative hypothesis is:

$$H_1: \beta_1 \neq \beta_2$$

This hypothesis will be tested at a two-sided 0.05 level.

To measure time in half-years the following formula will be used:

number of study days \* 
$$\left(\frac{2}{365.25}\right)$$

All efficacy measurements will be listed.

Descriptive statistics of actual values, changes from baseline and relative changes from baseline will be provided for FVC and FVC % predicted by treatment arm and visit. Descriptive statistics and listing of the estimated semiannual FVC rates of change will be provided as well.

To assess the effect of MN-001 as compared to Placebo based on FVC, change from baseline to Month 3 and change from baseline to Month 6 will be analysed within an analysis of covariance (ANCOVA) model respectively, with treatment as a fixed effect and baseline FVC as covariate. Least-squares means (LSM) for the change from baseline to Month 3 and Month 6 will be provided, including 95% Cls.

The same analysis will be repeated for FVC % predicted.

The analysis will be performed on the Full Analysis Set (FAS).

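### Does SAP 13.1 need to spell out the PROC MIXED settings for the primary FVC slope test?

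*SAP*

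**What the plan says.** SAP 13.1 makes the semiannual rate of FVC decline one of the primary endpoints. It specifies that "a random intercept, random slope linear mixed model will be fitted (using proc mixed in SAS"), with a common intercept, one slope per arm, and subject terms that "are random effects (random intercepts and slopes) for subject i". The null hypothesis is equal slopes (beta1 = beta2), and "This hypothesis will be tested at a two-sided 0.05 level". An estimator is named once, in the reason for not imputing: "Missing data will not be imputed because the ML-estimate is unbiased for this model in case of a Missing at Random (MAR) mechanism".

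For output, the same section says "Descriptive statistics and listing of the estimated semiannual FVC rates of change will be provided as well". For the separate ANCOVAs it says "Least-squares means (LSM) for the change from baseline to Month 3 and Month 6 will be provided", with 95% intervals. It requests no interval for beta1 - beta2.

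Protocol section 13 defers to the SAP: "The Statistical Analysis Plan (SAP) will provide comprehensive details on the statistical methods planned for this study". SAP 10.6 limits the weight of every test: "The results of all statistical tests (i.e., P values) will be interpreted descriptively, and no adjustment for multiple comparisons will be made".

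**The concern.** The protocol promises full detail in the SAP, yet three settings that determine the slope p-value are not written down: ML or REML for the test, the denominator degrees of freedom, and whether the random intercept and slope may correlate. With roughly 10 against 5 subjects and three FVC visits, none of these is negligible.

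ML does not allow for the estimated fixed effects when it estimates variances, so its standard error is too small in small samples. The only estimator the section names is ML. If a programmer took that remark as an instruction and also allowed a free covariance, a nominal 5% test could run at up to nearly 10%. Two programmers could both claim to follow the SAP and report different p-values for a primary endpoint.

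**Working it through.** **Inputs from the documents.** About 15 subjects, 2:1, taken as 10 and 5 (SAP 6.1 and 8). FVC at Day -7, Month 3 and Month 6 (SAP 5.2.1). Time in half-years is study days x 2/365.25 (SAP 13.1), so Day -7 is -14/365.25 = -0.038, and the later visits are about 0.5 and 1.0. Two-sided level 0.05. The documents give no power, effect size or variance, so there is no figure of the plan's own to reproduce.

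**Inputs assumed.** Intercept SD 0.7 L; slope SD 0.05, 0.12, 0.20 or 0.30 L per half-year; residual SD 0.05, 0.10 or 0.15 L; intercept-slope correlation -0.4, 0 or 0.4. That makes 4 x 3 x 3 = 36 combinations, with 10,000 null trials each (Monte Carlo error about 0.2-0.3 points).

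**Test.** t = (b1 - b2)/SE, where SE = sqrt(c'(X'V^-1 X)^-1 c) and c = (0, 1, -1). With complete data there are 15 x 3 = 45 observations, and X and Z together have rank 30, giving 45 - 30 = 15 df. With three Month 6 values missing, 42 - 30 = 12 df.

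**Hand check.** With complete data, think of one slope per subject. The unbiased variance divides by 15 - 2 = 13 and ML divides by 15, so the ML standard error is sqrt(13/15) = 0.931 of the right one. The 15-df critical value is 2.131, and 2.131 x 0.931 = 1.984. A t variable on 13 df exceeds 1.984 in absolute value 6.9% of the time. Without the ML shrinkage it exceeds 2.131 5.3% of the time. The simulated cell with slope SD 0.20, residual SD 0.10 and correlation 0 gives the same: 6.9% for ML and 5.3% for REML, both with zero covariance.

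**Simulated size of the nominal 5% test.**

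| Fit | Complete data (15 df) | 3 of 15 Month 6 values missing (12 df) |
|---|---|---|
| REML, zero covariance | 3.4-5.5% | 3.3-5.3% |
| REML, free covariance | 4.7-7.6% | 4.7-7.4% |
| ML, zero covariance | 4.1-7.3% | 4.2-6.8% |
| ML, free covariance | 5.8-9.4% | 5.9-9.6% |
| REML, Kenward-Roger, zero | 3.6-5.2% | 3.6-5.3% |
| REML, Kenward-Roger, free | 3.3-5.8% | 3.1-5.6% |

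The missing-data column covers 12 of the combinations (correlation 0). Fits with a zero slope variance or a correlation at its limit are included throughout.

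A second simulation, with separate code, intercept SD 0.75 L, residual SD up to 0.20 L and 14 scenarios, gave on 13-15 df: REML zero 3.3-5.7%, REML free 4.2-7.6%, ML zero 4.2-7.2%, ML free 5.6-9.5%.

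**Which row the plan leads to.** SAP 13.1 names the procedure and no options; SAP 10.8 fixes SAS 9.4 or above. That procedure's defaults are REML, uncorrelated random effects and containment degrees of freedom, which is the first row. This is a property of the software, not a statement in the SAP.

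**What writing in Kenward-Roger would add.** Compare the first row with the fifth: 3.4-5.5% against 3.6-5.2%. In seven combinations (1,500 null trials each), adding Kenward-Roger to REML with zero covariance widened the median interval by about 1.5%. It moved the p-value across 0.05 in 0.3-0.9% of trials.

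**The case for a change.** The strongest case for a change is that the SAP does not say the defaults apply, and the one estimator it names is ML. In the simulations, ML with free covariance and REML with zero covariance fell on opposite sides of 0.05 in 2.6-5.5% of null trials. With complete data, the ML standard error under free covariance is 8-16% too small. A planner who carried it forward would understate the variance of the slope difference by 1 - 0.92^2 = 15% to 1 - 0.84^2 = 29%, and SAP section 8 says this pilot is meant to inform later designs.

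Part of this stands. The settings are not written down, and a free covariance is a natural choice for a random-slope model; even under REML it can reach 7.6%. Degrees of freedom matter too: on 42 residual df, REML with zero covariance gives 4.7-6.7%.

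The rest is weaker. The ML remark explains why missing values are left alone. The same argument covers any likelihood-based fit, REML included, so the sentence does not require ML for the test. The 2.6-5.5% and 15-29% figures use ML with a free covariance, a structure the SAP never mentions. Against the default fit the difference is slight. The absent interval for beta1 - beta2 is a reporting preference, since the planned model yields it directly. SAP 13.3 writes out no hypothesis test for the 6-minute walk rates, so the point has no added force there.

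**Conclusion.** No change is needed. The gap is real but is one of documentation: run as named, the procedure gives a test with size of about 3-6%, and writing the settings out also gives about 3-6%. Inflation to about 4-7% or 6-10% requires ML, with zero or free covariance respectively; REML with a free covariance lies between, at about 4-8%. These figures hold for reference df of about 12-15, 10 against 5 subjects, normal data and the assumed variances.

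The consequence is small in any case. P-values are descriptive and unadjusted, no interim analysis is planned, and no power is claimed. The largest mean error of the ML slope difference in the runs was 0.003 L, so the estimate itself is not in question. The FVC and FVC % predicted ANCOVAs, with their own 95% intervals, do not depend on these settings. The conclusion would be different if the slope p-value were confirmatory, or if the SAP had prescribed ML with an unstructured covariance.

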**Idiopathic Pulmonary Fibrosis** 

 $\varepsilon_{ij}$  is a random error term

The following null hypothesis (equal mean rates of change) will be tested within this model:

$$H_0: \beta_1 = \beta_2$$

The alternative hypothesis is:

$$H_1: \beta_1 \neq \beta_2$$

This hypothesis will be tested at a two-sided 0.05 level.

To measure time in half-years the following formula will be used:

number of study days \* 
$$\left(\frac{2}{365.25}\right)$$

All efficacy measurements will be listed.

Descriptive statistics of actual values, changes from baseline and relative changes from baseline will be provided for FVC and FVC % predicted by treatment arm and visit. Descriptive statistics and listing of the estimated semiannual FVC rates of change will be provided as well.

To assess the effect of MN-001 as compared to Placebo based on FVC, change from baseline to Month 3 and change from baseline to Month 6 will be analysed within an analysis of covariance (ANCOVA) model respectively, with treatment as a fixed effect and baseline FVC as covariate. Least-squares means (LSM) for the change from baseline to Month 3 and Month 6 will be provided, including 95% Cls.

The same analysis will be repeated for FVC % predicted.

The analysis will be performed on the Full Analysis Set (FAS).

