7.3. Subject Withdrawal/Discontinuation Criteria

Subjects may request to be withdrawn from the study at any time for any reason.

The Investigator may interrupt the treatment of any subject whose health or well-being may be compromised by continuation in the study. The following instances require subjects to be withdrawn from the study:

- Subject fails to adequately comply with the dosing, evaluations, or other requirements of the study at the discretion of Investigator.
- Subjects who have adverse events that require discontinuation of study medication;

- Subjects who, in the opinion of the Investigator, should be discontinued for their wellbeing;
- Subjects who start Esbriet® (Pirfenidone) or OFEVTM (Nintedanib) during the study.
- Subjects who are no longer able to understand task instructions or to perform tests adequately.
- Subject becomes pregnant during the study. See section 12.7 for reporting requirements and follow-up of the pregnancy.

If a subject withdraws or is removed from the study for any reason, the reason and date of discontinuation of study medication should be recorded in the appropriate section of the Case Report Form (CRF). At the time of study discontinuation, every effort should be made to ensure all Early Termination (ET) procedures and evaluations are performed.

The study sponsor reserve the right to discontinue the study at any time for medical or administrative reasons.

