#### 6. STUDY METHODS

### 6.1. Overall Study Design and Plan

This is a randomized, placebo-controlled, double-blind 6-month study followed by a 6-month open-label extension phase to evaluate the efficacy, safety, and tolerability of MN-001 in moderate to severe IPF patients. MN-001 750 mg or matching Placebo will be orally administered twice daily over a 26-week period in subjects with a confirmed diagnosis of moderate to severe IPF per the ATS 2011 Guidelines (Raghu et al, 2011).

Approximately 15 subjects are planned to be enrolled. This study will consist of two treatment arms, MN-001 and matching Placebo. Randomization will occur in a 2:1 ratio (MN-001:Placebo). Eligible subjects will consist of males and females ranging in age from 21 to 80 years old, inclusive. The study will consist of a Screening Phase (up to 3 months prior to Day 1) followed by a 26-week double-blind Treatment Phase, a 26 week Open-Label Extension (OLE) phase and a Follow-up Visit (within 4 weeks after the last dose).

Overall study design and plan is described in detail in Final Protocol Amendment 1, Section 6. Overall Study Design and plan: Description.

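### The Month 6 ANCOVAs for FVC and FVC % predicted drop anyone without a Month 6 value, fall outside the SAP's missing-at-random argument, and can be biased if exit depends on Month 3 FVC

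*SAP*

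**What the plan says.** SAP 13.1 names three kinds of primary endpoint: change in FVC, change in FVC % predicted (each absolute and relative), and the semiannual rate of decline in FVC. It plans two kinds of between-arm model.

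- **Slope.** A random-intercept, random-slope mixed model is fitted to FVC from baseline to Month 6. On missing data the SAP says: "Missing data will not be imputed because the ML-estimate is unbiased for this model in case of a Missing at Random (MAR) mechanism". The equal-slopes hypothesis follows, with "This hypothesis will be tested at a two-sided 0.05 level".
- **By visit.** For FVC, "change from baseline to Month 3 and change from baseline to Month 6 will be analysed within an analysis of covariance (ANCOVA) model respectively". The terms are treatment and baseline FVC, and LS means with 95% CIs are reported. The next sentence repeats this for FVC % predicted. No missing-data rule is given for these models.

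Related text:

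- SAP 9 admits a subject to the Full Analysis Set (FAS) after one dose and one later efficacy assessment.
- SAP 13.2 plans two subset analyses: subjects without major deviations, and valid completers.
- SAP 10.4 adopts the protocol visit windows. No rule assigns an early-termination test to Month 6.
- SAP 10.6: "The results of all statistical tests (i.e., P values) will be interpreted descriptively, and no adjustment for multiple comparisons will be made".
- Protocol 7.3 requires withdrawal of, among others, "Subjects who start Esbriet® (Pirfenidone) or OFEVTM (Nintedanib) during the study".
- Protocol 8.8.1.4 asks for pulmonary function at early termination unless it was tested within the previous month.

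**The concern.** The words "Missing data will not be imputed because the ML-estimate is unbiased for this model in case of a Missing at Random (MAR) mechanism" justify one model, and a different model then produces the by-visit primary estimates. With no imputation and no Month 3 term, the Month 6 ANCOVA uses only subjects who have a Month 6 value. It is unbiased if, given arm and baseline FVC, having that value is unrelated to the Month 6 outcome. The slope model needs less, because it keeps the Month 3 value of a subject who leaves later.

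Exit that depends on Month 3 FVC is plausible. A subject with a poor Month 3 test might start an approved antifibrotic and would then have to be withdrawn. With about 5 placebo subjects, one or two such exits remove 20% to 40% of that arm at Month 6.

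The Month 6 estimate for each measure is at stake. For FVC % predicted it matters more, since the ANCOVA is the only between-arm model written for that measure. SAP 8 says the results will be used to design later studies, so the estimates count for more than the p-values.

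**Working it through.** **Inputs from the documents.** "Approximately 15 subjects are planned to be enrolled", randomised 2:1, so 15 × 2/3 = 10 on MN-001 and 15 × 1/3 = 5 on placebo. Double-blind spirometry is at screening, Month 3 and Month 6. The documents give no effect size, SD, power or dropout rate, so there is no figure of the plan's to reproduce.

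**Assumed inputs.** Baseline SD 0.7 L; placebo decline 100 mL per half-year; true Month 6 difference 0 or 100 mL. Three settings of slope SD and error SD, in mL: A = 120 and 80, B = 200 and 100, C = 200 and 50. Exit after Month 3 has logit −1.4 − 1.5z, where z is the standardised Month 3 change. This gives 19% to 27% exit in an affected arm.

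**Why the ANCOVA can be biased.** Let C3 and C6 be the changes to Months 3 and 6. In each arm, the mean C6 of those who stay is shifted by

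shift = k × m × SD(C3),

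where k = cov(C3, C6)/var(C3) = (0.5·slope SD² + error SD²)/(0.25·slope SD² + 2·error SD²), and m is the mean standardised C3 of the stayers relative to their own arm. (The small correlation of C3 with measured baseline is ignored here.) Then

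bias = shift(MN-001) − shift(placebo).

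If exit is unrelated to C3, m = 0 and there is no bias. If the same rule acts in both arms and there is no treatment effect, the shifts cancel. Otherwise they do not.

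**By hand.** Under the exit rule above, m = 0.295 in the placebo arm. If only placebo subjects leave:

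- A: k = 0.829, SD(C3) = 128 mL, bias = −0.829 × 0.295 × 128 = −31 mL
- B: k = 1.0, SD(C3) = 173 mL, bias = −51 mL
- C: k = 1.5, SD(C3) = 122 mL, bias = −54 mL

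**Simulated large-sample bias of the Month 6 ANCOVA (mL, 600,000 subjects per run).**

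| Exit after Month 3 | True difference | A | B | C |
|---|---|---|---|---|
| Common rule | 0 | 0 | −1 | −0.5 |
| Common rule | 100 | −7 | −10 | −14 |
| Placebo only | 0 | −32 | −52 | −55 |
| Placebo only | 100 | −32 | −52 | −55 |
| MN-001 only | 0 | +31 | +52 | +54 |
| MN-001 only | 100 | +23 | +41 | +41 |

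Exit unrelated to FVC gave bias within 1 mL. The Month 3 ANCOVA stayed within 1 mL of the truth throughout.

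**The joint estimate.** Regress C6 on treatment, baseline and C3 among stayers. Then add (coefficient of C3) × (Month 3 treatment difference in all subjects) to the treatment coefficient. This is the likelihood estimate for the two visits with unstructured covariance. It was within about 2 mL of the truth in every large-sample run.

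**At 10 v 5 (setting B, up to 20,000 trials per case).** Excluding the few trials with almost no Month 6 data in an arm:

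- ANCOVA bias: about −1 mL (common rule, no effect), −11 mL (common rule, 100 mL effect), and 40 to 51 mL in size for one-arm exit.
- RMSE: 151 to 165 mL for the ANCOVA, 146 to 162 mL for the joint estimate, about 139 mL with no dropout.

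The worst bias is thus about a third of the sampling error (51/155 ≈ 0.33).

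**Sensitivity to the exit rule.** Under a cut-off rule, subjects with a fall of more than 100 mL leave with probability 0.5 to 0.8. The true difference is 100 mL, slope SD 100 to 200 mL, error SD 80 to 100 mL.

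| Fall measured at | Who leaves | ANCOVA mean (mL) | Joint-model mean (mL) |
|---|---|---|---|
| Month 3 | Both arms | 82–97 | 100–101 |
| Month 3 | Placebo only | 15–75 | 98–102 |
| Midway between Months 3 and 6, value not analysed | Both arms | about 76–92 | about 89–96 |
| Midway between Months 3 and 6, value not analysed | Placebo only | about 5–75 | about 63–89 |

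With exit triggered at Month 3, the SD of the estimate at 10 v 5 was 107 to 153 mL for the ANCOVA and 107 to 151 mL for the joint model.

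**The case against.** The strongest reply has five parts.

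- **The FVC comparison that is formally tested is already protected.** This stands. The slope model is the only FVC analysis with a stated hypothesis and level, and it uses Month 3 data from later leavers. A reader might infer that the primary FVC test is invalid; the SAP does not support that. It does not help FVC % predicted, because the slope model is written for FVC only.
- **The exit mechanism is conjecture.** This stands in part. No text links starting an antifibrotic to an FVC fall or gives a rate, and subjects on stable nintedanib may enrol. The explicit individual stopping triggers (Protocol 7.3.1) are gastrointestinal and have no documented link to FVC. Blinding also makes a rule confined to one arm less likely, so the one-arm cases bracket the bias and do not forecast it.
- **Complete-case analysis is inferred.** True: the SAP never uses the term. An early-termination test may also exist for someone who left between Months 3 and 6. But the SAP has no rule for entering that test at Month 6, so the gap remains.
- **The alternative is not fully protected either.** This stands. If exit follows a fall that is not in the analysed data, the two-visit model is biased too, though less than the ANCOVA.
- **The gain is small for a pilot of 15 with descriptive p-values.** Fair for precision, since RMSE barely moves. But the model uses data already collected and did no worse in any case run.

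A reader might also put any disagreement between the slope model and the ANCOVA down to dropout. That does not follow: the slope model also imposes linearity and a common intercept and uses actual times, so the two can differ with complete data.

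**Conclusion.** The gap is real but conditional. The SAP's no-imputation argument does not reach the Month 6 ANCOVAs for FVC and FVC % predicted, and neither subset in SAP 13.2 recovers the excluded subjects. Whether bias follows depends on why subjects leave. It is about zero if exit is unrelated to FVC, or if a common rule acts with no treatment effect. It is 7 to 14 mL towards zero with a common rule and a 100 mL effect. It is 23 to 55 mL, against or in favour of MN-001, if only one arm loses its decliners. A harsher cut-off rule confined to placebo gives more, up to about 95 mL, still below the sampling SD at 10 v 5.

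A reader might conclude that the Month 6 difference is biased, or that both ANCOVAs are. The documents support neither: they give no dropout pattern, and exits after Month 3 leave the Month 3 ANCOVA unchanged. Every size rests on assumed variances, effect and exit rules. This is a worthwhile, inexpensive improvement to two primary estimates, not a fault that invalidates the plan.

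**What to change.** In SAP 13.1, replace the two ANCOVAs with one repeated-measures likelihood model for change at Months 3 and 6.

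- Terms: treatment-by-visit and baseline-by-visit. Use an unstructured 2×2 covariance with a simpler structure prespecified as fallback, and REML with Kenward-Roger degrees of freedom.
- Report the MN-001 minus placebo contrast with 95% CI at each visit.
- Do the same for FVC % predicted.
- Keep the by-visit ANCOVAs as sensitivity analyses.
- State how early-termination spirometry enters the by-visit analysis, including when, if ever, it counts as Month 6.

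The cost is SAP wording and a few lines of PROC MIXED. With complete data the point estimates equal those of the ANCOVAs. The downside is six fixed effects and three covariance parameters on at most 15 × 2 = 30 observations, hence the fallback. The model removes the bias fully only if exit depends on FVC values that it includes, and the report should say so.
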